PSA kinetics: The relationship between the log of PSA and time of PSA measurement will be estimated from a piecewise linear regression model: $\log(PSA) = \alpha_1 + \alpha_2(POST) + \beta_1(Time) + \beta_2(Time \times POST)$, where POST=1 if post treatment initiation, and 0 if pre-enrollment. Pre- and Post-treatment PSA slope will be estimated for each patient (β_1 and $\beta_1 + \beta_2$, respectively). PSA-DT will be computed as the natural log of 2 divided by the estimated slope.

Response: The primary end point is changes in PSA doubling time (PSA-DT) computed at 9 months compared to pre-treatment PSA-DT. Response to treatment will be defined as the lengthening of PSA-DT at 9 months from pre-treatment PSA-DT by > 3 months. Secondary outcomes include safety and other measures of response such as the proportion of patients achieving a PSA decline of $\geq 50\%$ in the highest measured pre-treatment PSA.

Statistical methods (High Risk surgical cohort):

PSA kinetics: The patients in the surgical cohort all have non-detectable pre-treatment PSA levels however are considered at a higher risk for relapse based on surgical parameters such as surgical margins, age, and Gleason scores.

Response: The primary end point is the maintenance of undetectable PSA levels achieved post-surgery for a minimum of 9 months. Response to treatment will be defined as a PSA of < 0.20 at 9 months. Secondary outcomes include safety and PSA slope (if rising PSA levels observed).

Trial Design and sample size considerations: For each patient group (surgical, rising PSA surgical, radiation), a single arm Phase II trial of the same treatment regimen will be conducted in parallel. For each, Simon's two-stage optimal design will be used with the following assumptions: an ineffectiveness cutoff of 10%; a clinically relevant response rate of at least 30%; type I error rate of 0.05; type II error rate of 0.10. Given these parameters, **a total of 18 patients will be enrolled at the first stage of the trial**. Based response defined as a PSA-DT change > 3 months, if 2 or fewer responses are observed, the study will be terminated at the first stage. However if at least 3 responses are observed in the set of 18 patients, an additional 17 patients will be enrolled in the second stage, for **a total of 35 patients enrolled**. At the end

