of the second stage, if 6 or fewer responses are observed then the treatment will be declared ineffective. Otherwise, the study is considered to have achieved the targeted response rate. Under this optimal design, the probability of early stopping given an ineffective treatment is 0.73.

Primary Endpoints

- Increase PSA Doubling Time
- Decrease PSA Levels (% PSA decline)

Secondary Endpoints:

- Determine time to secondary therapy for prostate cancer upon PSA recurrence
- Time to Cancer Progression
- Salvage therapy outcomes after treatment with Metformin
- Determine the safety and incidence of serious adverse events from the administration of 9 months of metformin to men with high risk prostate cancer and prostate cancer with rising PSA post-treatment.

Number of Subjects

Stage 1: 18 High Risk Surgical patients, 18 Rising PSA Surgical Patients, 18 Radiation patients

Stage 2 (if Stage 1 deemed successful): 17 High Risk Surgical Patients, 17 Rising PSA Surgical patients, 17 Radiation patients

Gender of Subjects

All subjects included in this study will be male.

Age of Subjects

Subjects will be at least 18 years or older.

Racial and Ethnic Origin

Subjects will be recruited from all racial and ethnic groups.

Inclusion/Exclusion Criteria

Inclusion Criteria:

- 1) Must be male > 18 years of age
- 2) Biopsy confirmed adenocarcinoma of the prostate.
- 3) Radiation Patients: Rising serum PSA for on ≥ 3 time points at least 1 month apart, after Nadir has been reached. Must be at least 18 months since last radiation treatment. PSA-DT must be > 6 months.
- 4) High Risk Surgical Patients: patients who have had radical prostatectomy and:
 - a) High Risk based on Surgical Pathology (Patients have any of the following: \geq Gleason 8 or higher, Extra-capsular extension, positive surgical margins, or seminal vesicle invasion)
 - b) Undetectable PSA
- 5) Rising PSA Surgical Patients: Patients who have had radical prostatectomy and:
 - a) Rising serum PSA for ≥ 3 time points at least 1 month apart
 - b) Unwilling or medically unfit for salvage Radiation Therapy
- 6) Able to swallow and retain oral medication
- 7) Hemoglobin A1c $\leq 7.0\%$
- 8) Able and willing to participate in the full 12 months of the study
- 9) Able to understand instructions related to study procedures
- 10) Able to read and write (health outcome questionnaires are self-administered), understand instructions related to study procedures and give written informed consent

Exclusion Criteria:

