If study participants experience any of the following while receiving Metformin treatment, they will be removed from the study and referred for alternative treatment such as Androgen Deprivation Therapy, Salvage Cryotherapy for radiation patients, or Salvage Radiotherapy:

- High Risk Surgical Patients: PSA level rises 0.6ng/mL from baseline
- Rising PSA and Radiation Patients: PSA Doubling Time accelerates below 6 months

These participants will be removed from the intervention arm of the study, but will continue to be followed for disease outcome and quality of life for three years following removal from the study.

Data Analysis and Data Monitoring

The Winthrop University Hospital Department of Biostatistics has been consulted during the development process of this protocol, and will be consulted for statistical analysis of PSA kinetics, adverse events, and overall outcome.

The research coordinator will review study conduct including informed consent procedures, accrual, drop-outs, protocol deviations and AEs in aggregate on a monthly basis. The principal and sub-investigators review serious adverse events (SAEs), and laboratory results monitoring

in real-time. The research coordinator, research fellow and study investigators will review study subject compliance with study procedures on a three month basis.

Study data are provided to the research coordinator and study investigators prior to each monthly review by the research fellow. Data reports for end of phase analysis are prepared by the study statistician, [name].

The research coordinator provides a written report to the study team with recommendations for study modification, study continuation/discontinuation as relevant. After the report is generated, the coordinator will meet with the study investigators to discuss relevant findings.

The study team is responsible for forwarding the report to the IRB.

Analysis of Adverse Events

Adverse events will be monitored on an ongoing monthly basis throughout the duration of the study, and the rates will be formally analyzed at the end of the first stage of the study as outlined in the statistical methods section of the protocol.

Analysis of Serious Adverse Events

Serious adverse events will be monitored in real time, and the rate of subjects experiencing these events will be analyzed every month as needed as the study progresses.

Analysis of Efficacy

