The primary end points for efficacy for each study cohort will be analyzed at the end of the first stage of the study (total accrual 18 patients, 9 months of treatment).

- Efficacy in the Rising PSA Surgical and Radiation Cohorts: Response to treatment is defined as a lengthening of PSA doubling time from pre-treatment PSA doubling time by >3 months at the end of the 9 months of treatment.
- Efficacy in the High Risk Surgical Cohort: Response to treatment is defined as PSA level of <0.20ng/mL at the end of the 9 months of treatment.
- Secondary Efficacy in Rising PSA Surgical and Radiation Cohorts: The proportion of patients achieving a PSA decline of $\geq 50\%$ from the highest measured pre-treatment PSA.

Data Storage and Confidentiality

Data will be stored in our HIPAA-compliant case report form database. Only the study investigators, research coordinator, research fellow, and biostatistician will be provided with

access information to the database. A unique non-identifying code will be assigned to each study participant.

RISK/BENEFIT ASSESSMENT

Risk

Expected AEs

Expected AEs associated with Metformin include:

- Hypoglycemia (10% of diabetic patients)
- Diarrhea (9.6% of diabetic patients)
- Nausea/Vomiting (6.5% of diabetic patients)
- Constipation (Between 1-5% of diabetic patients)
- Weight loss (14% of metastatic prostate cancer patients)
- Fatigue (18% of metastatic prostate cancer patients)

Rare but Serious AEs

Rare but serious AEs that may be associated with Metformin include:

- Lactic Acidosis: approximately 0.03 cases/1000 patient-years, with approximately 0.015 fatal cases/1000 patient-years

AE Management

The rate of expected adverse events cannot be definitively predicted in this population of patients. Adverse events will be recorded and monitored throughout the study, and the rates will be reported as part of the study end points. Subjects who cannot tolerate adverse events will be removed from the study at the request of the subject or at the discretion of the investigators.

Study subjects will be screened for known risk factors of Metformin associated lactic acidosis and will be excluded from enrollment in the study if any risk factors are found. If lactic acidosis occurs in a study subject while on Metformin, the subject will be immediately removed from the study.

ADDENDUM:

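### Seven or more responses in 35 rules out a response rate of 10% or less, but the protocol words this as achieving an undefined target, most naturally 30%

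*Combined protocol and SAP*

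**What the plan says.** The paragraph on trial design and sample size in the combined protocol and SAP uses Simon's optimal two-stage design separately for each of the three patient groups. It sets two rates, both in per cent: "an ineffectiveness cutoff of 10" and "a clinically relevant response rate of at least 30". The error rates are a "type I error rate of 0.05" and a "type II error rate of 0.10". Stage 1 has 18 patients and stops at 2 or fewer responses. Stage 2 adds 17, for 35 in total.

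At the end of stage 2, "if 6 or fewer responses are observed then the treatment will be declared ineffective". The next sentence gives the only positive conclusion in the plan: "Otherwise, the study is considered to have achieved the targeted response rate". The target it mentions is named nowhere else and is not defined.

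Two other sections bear on the final analysis, and neither limits this conclusion:

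- Analysis of Efficacy is tied to the interim look: "The primary end points for efficacy for each study cohort will be analyzed at the end of the first stage of the study".
- Data Analysis and Data Monitoring assigns the reporting ("Data reports for end of phase analysis are prepared by the study statistician") but specifies no estimate, interval or wording for the conclusion.

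**The concern.** A two-stage design of this kind tests one hypothesis, that the response rate is no higher than the ineffectiveness cutoff. The 30% rate enters only through the power: it is the rate at which the trial should be likely to pass. Passing therefore supports the statement that the rate is above 10%. It does not by itself support the statement that the rate is 30%.

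The protocol's sentence says that a rate has been achieved. A rate labelled as the ineffectiveness cutoff cannot sensibly be a target, which leaves 30% as the only stated candidate. On that reading, the plan lets a cohort with an observed rate of 20% be reported as having reached the clinically relevant rate. If the phrase is only a label for passing, the plan does not say what a positive result means.

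These are single-arm trials with no planned confidence interval for the response rate, so nothing else in the plan would show a reader how far a passing result may lie below 30%.

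**Working it through.** **Inputs, all from the trial design paragraph.** Cutoff p0 = 0.10; clinically relevant rate p1 = 0.30; stage 1 size 18, stop at 2 or fewer; total 35, ineffective at 6 or fewer. The type I error is taken as one-sided, as is inherent in Simon's design; the protocol does not state the side.

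**Formulas.** With X1 ~ Bin(18, p) and X2 ~ Bin(17, p), independent:

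- P(stop early | p) = P(X1 ≤ 2)
- P(pass | p) = Σ over x1 = 3 to 18 of P(X1 = x1) × P(X2 ≥ 7 − x1)

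**1. The plan's own figures.** At p = 0.10, P(stop early) = 0.1501 + 0.3002 + 0.2835 = 0.7338; the protocol states 0.73. P(pass | 0.10) = 0.0474, within the 0.05 limit. P(pass | 0.30) = 0.9016, so the type II error is 1 − 0.9016 = 0.0984, within the 0.10 limit. A search over designs meeting these limits, for the smallest expected sample size at 10%, returns 2/18 and 6/35 (expected size 18 + 17 × (1 − 0.7338) = 22.5). The design is the one the protocol says it is.

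**2. What passing excludes.** P(pass | p) = 0.05 at p = 0.1012. At one-sided 0.05, the smallest passing result thus excludes rates up to about 10.1% and no higher.

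**3. The smallest passing result.** 7/35 = 20.0%. For an interval that respects the two stages, outcomes are ordered with stage 1 stops lowest and then by total responses.

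- Lower limit: the p at which P(X1 ≥ 3 and total ≥ 7) = 0.05, which is 0.1012.
- Upper limit: the p at which P(stage 1 stop, or total ≤ 7) = 0.05, which is 0.3539.

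The 90% interval, matching the one-sided 0.05 test, is 10.1% to 35.4%.

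**4. Passing results with an observed rate below 30%.** 30% of 35 is 10.5, so these are 7 to 10 responses: 7/35 = 20.0%, 8/35 = 22.9%, 9/35 = 25.7%, 10/35 = 28.6%.

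**5. How often a regimen below 30% would be said to have achieved the target.**

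| True response rate | P(stop early) | P(pass) |
|---|---|---|
| 10% | 0.734 | 0.047 |
| 15% | 0.480 | 0.234 |
| 20% | 0.271 | 0.516 |
| 25% | 0.135 | 0.759 |
| 30% | 0.060 | 0.902 |

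The rows for 15% to 25% measure the problem. These true rates lie between the two design rates, where the rule passes often, as it is built to do, and where the protocol's sentence would then overstate the result.

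**The case against.** The strongest reply is that this concerns one label. The rule has two outcomes, the sentence names the second, and its wording can be read as a decision label, not as an estimate. The paragraph gives both rates and both error rates just before, so a statistical reader can see what is tested. No bound, sample size or treatment decision depends on the phrase, and reading the target as 30% is an inference. All of this stands, and it is why the point is minor. It does not remove the point: if the phrase is only a label, the plan's one positive conclusion still lacks a stated meaning, and the same sentence repairs it.

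It can also be said that the rule is worded for doubling-time response, which does not fit the High Risk Surgical cohort, and that a count as low as 7 to 10 seems unlikely in patients who start with undetectable PSA. The documents give no expected rate for that cohort, so the second part is an assumption. The protocol applies the design to each group, so the sentence covers all three.

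A reader might infer more than the documents support:

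- *That the design is wrong or the final bound too low.* It is not; 2/18 and 6/35 is the optimal design for the stated inputs.
- *That the trial must prove a rate above 30%.* The protocol sets no such aim, and the design was not built for it.
- *That a result of 7/35 contradicts 30%.* It does not; the interval of 10.1% to 35.4% contains 30%. The result only fails to establish it.
- *That the share of low passes at a true rate of 30% measures the harm.* At that rate the regimen does have the target rate, so saying so would not be false.

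**Conclusion.** The point holds as a minor one. The design is right for 10% versus 30%; the conclusion attached to passing goes further than the test. Passing rejects a response rate of 10% or less (type I error 0.047) and does not show 30%. The smallest pass is an observed 20.0%, and regimens truly at 15%, 20% and 25% would pass with probability 0.234, 0.516 and 0.759.

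This rests on two assumptions. First, the undefined target means 30%, which is the only stated rate that fits but is not certain; a reader might take the sentence as a definite claim that 30% is proven, and the documents do not go that far. Second, each cohort is analysed at the planned 18 and 35 patients with the stated bounds.

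**What to change.** Replace the sentence that follows the final bound with:

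> If 7 or more responses are observed in 35, the hypothesis of a response rate of 10% or less is rejected; the observed response rate is reported with a confidence interval that allows for the two-stage design.

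This drops the undefined target and states what the test supports. The interval is a small added reporting duty; it lets a reader see how far a passing result is compatible with rates below 30%.

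The cost is one sentence in the protocol. Bounds, sample size and error rates do not change. The downside for the sponsor is a less favourable permitted conclusion.

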1. Metastatic Disease

2. PSADT < 6 months
3. Subject that has ever been treated for prostate cancer with any of the following:
 - Chemotherapy
 - Hormonal therapy (e.g., megestrol, medoxyprogesterone, cyproterone)
 - Oral glucocorticoids
 - GnRH analogues (e.g., leuprolide, goserelin, degarelix)
 - Previous treatment with GnRH analogues is allowed after a wash out of at least one month and a return to normal serum Testosterone levels
4. Current and/or previous use of the following medications:
 - Use of 5 α -reductase inhibitors (eg. Finasteride, Dutasteride) within the past 6 months of screening
 - Drugs with antiandrogenic properties (e.g., flutamide, bicalutamide, ketoconazole, progestational agents) within 6 months prior to screening
 - Diagnosis of Type 1 Diabetes Mellitus
 - Exposure to metformin within 12 months of screening
 - Planned or concurrent use of any oral or injectable diabetes drug
 - Known hypersensitivity or intolerance to metformin hydrochloride
5. Any condition associated with increased risk of metformin hydrochloride-associated lactic acidosis
6. Participation in any investigational or marketed drug trial within 30 days prior to screening or anytime during the study period. This includes any interventional or exercise trials.
7. Any unstable serious co-existing medical condition(s) including, but not limited to, myocardial infarction, coronary bypass surgery, unstable angina, cardiac arrhythmias, clinically evident congestive heart failure, or cerebrovascular accident within 6 months prior to Screening visit.
8. History of megaloblastic anemia.
9. Abnormal liver function test:
 - Total bilirubin > institutional upper limit of normal (ULN)
 - Aspartate aminotransferase (AST) > institutional ULN
 - Alanine aminotransferase (ALT) > institutional ULN
 - Alkaline phosphatase (ALP) > institutional ULN

- Serum creatinine > institutional ULN

10. History of other malignancies, with the exception of adequately treated nonmelanoma skin cancer, stage I melanoma, NMIBC or other solid tumors curatively treated with no evidence of disease for at least 5 years
11. History or current evidence of substance abuse, as defined in DSM-IV, within 12 months of screening
12. History of any illness (including psychiatric) that, in the opinion of the investigator, might confound the results of the study or pose additional risk to the subject

Vulnerable Subjects

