No subjects from vulnerable populations (children, pregnant women, incarcerated persons) will be recruited for this study.

METHODS AND PROCEDURES

Pre-Enrollment Evaluation

1. Personal Medical History, including medication history, alcohol and tobacco use
2. Physical Examination including ECOG status, blood pressure, pulse, height, weight and BMI.
3. Hematology and Serum Chemistry, Liver Panel, total and free PSA, Testosterone level, Hemoglobin A1C, Insulin levels.
4. Tumor Characteristics, including Gleason score, tumor grade, MRI results (if available), biopsy results
5. List of previous prostate cancer treatment, any previous radiation treatment (for any disease condition).
6. PSA Kinetics: current PSA doubling time, record of all PSA tests in the year prior to enrollment
7. Completion of two study questionnaires for baseline disease related anxiety and quality of life: MAX-PC and EPIC.

Study Interventions

1. Upon study initiation, patient will receive two weeks of 750mg Metformin Extended Release (ER) to assess any adverse reactions.
2. After two weeks, patient will receive two doses of 750mg Metformin Extended Release (ER) per day for 8 months, two weeks.
3. Patients will receive Metformin Extended Release (ER) from the Principal or Sub-Investigators free of charge.

4. The study drug, 750mg Metformin Extended Release (ER), will be stored in the Principal Investigator's practice in a separate locked safe accessible only to research study personnel.

Study Evaluations

Patients will return to the Principal Investigator's practice every three months for evaluation of study compliance, completion of study questionnaires, and blood draw.

- a) Study subjects will be required to bring the medication bottle with them on each study visit and will also be required to sign an attestation that they are taking the medication as per study protocol.
- b) Study subjects will also submit a blood sample for evaluation of hematology and serum chemistry, insulin levels, total and free PSA, and Hemoglobin A1C.
- c) Study subjects will complete two questionnaires, the Expanded Prostate Cancer Index Composite (EPIC) to evaluate Prostate Cancer specific symptoms, and the Memorial Anxiety Scale for Prostate Cancer (MAX-PC) for evaluation of disease and treatment related anxiety.
- d) At the end of the study, at approximately 9 months, subjects will also be tested for insulin and testosterone levels.

Study Exit Procedures

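### High Risk Surgical cohort: radiotherapy before or during the study is not excluded, and a month-9 PSA <0.20 counts as a metformin response whatever other cancer treatment was given

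*Combined protocol and SAP*

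**What the plan says.** **Entry.** Inclusion Criterion 4 opens with "High Risk Surgical Patients: patients who have had radical prostatectomy and" and adds two conditions: at least one adverse pathology feature and an undetectable PSA. It does not say what made the PSA undetectable.

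**Exclusions.** Exclusion Criterion 3 opens with "Subject that has ever been treated for prostate cancer with any of the following" and lists chemotherapy, hormonal therapy, oral glucocorticoids and GnRH analogues. Radiotherapy is not on the list or in any other exclusion. For GnRH analogues the same criterion adds: "Previous treatment with GnRH analogues is allowed after a wash out of at least one month and a return to normal serum Testosterone levels". Exclusion Criterion 4 bars antiandrogenic drugs "within 6 months prior to screening".

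**The other cohorts.** Both carry a radiotherapy condition. Criterion 3 (Radiation) says "Must be at least 18 months since last radiation treatment". Criterion 5b (Rising PSA Surgical) says "Unwilling or medically unfit for salvage Radiation Therapy".

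**Endpoint.** Statistical methods (High Risk surgical cohort) states: "The primary end point is the maintenance of undetectable PSA levels achieved post-surgery for a minimum of 9 months". That section and Analysis of Efficacy then define response as PSA <0.20 at 9 months, with no condition on other treatment.

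**Data collected.** Pre-Enrollment Evaluation, item 5, records "List of previous prostate cancer treatment, any previous radiation treatment (for any disease condition". No eligibility or analysis rule for this cohort uses it.

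**The concern.** The endpoint wording presumes a PSA made undetectable by surgery, but the entry and response rules do not enforce that. As written, three kinds of men can be enrolled and counted as responders: a man who has just completed adjuvant radiotherapy; a man whose PSA recurred and became undetectable again after salvage radiotherapy; and a man who starts radiotherapy during the 9 months.

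Each cohort is a single-arm trial judged against a fixed response rate, so there is no comparison group in which the effect of radiotherapy would cancel. A PSA held below 0.20 by radiotherapy is credited to metformin. At stake are the estimated response rate, the go/no-go decision, and the meaning of any reference rate the sponsor later adopts.

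**Working it through.** **1. Is there a rule elsewhere that closes the gap?**
- Exclusion 6 bars other trials, not standard care. Exclusion 12 concerns illness, not treatment.
- Study Exit Procedures gives one trigger for this cohort, a PSA rise of 0.6 ng/mL. Starting another cancer therapy is not a trigger.
- A man removed at that trigger is referred for other treatment and still followed. Nothing says how a later PSA <0.20 would be counted.

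No section closes the gap.

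**2. Reproduce the design.** Inputs from Trial Design and sample size considerations: null 0.10, target 0.30, type I error 0.05, type II error 0.10; continue if at least 3 of 18 respond; success if at least 7 of 35 respond. I apply these bounds to this cohort's own response, PSA <0.20 at month 9.

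P(stop at stage 1) = P(X1 ≤ 2), with X1 ~ Bin(18, p).

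P(success) = Σ over x = 3 to 18 of P(X1 = x) × P(X2 ≥ 7 − x), with X2 ~ Bin(17, p).

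- p = 0.10: early stopping 0.734 (plan: 0.73); P(success) 0.047.
- p = 0.30: P(success) 0.902.

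The design arithmetic is correct.

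**3. Contamination under the plan's own null, inert drug.** Let f be the share of men whose PSA is controlled by another treatment and c their chance of PSA <0.20 at month 9. The documents give neither, so both are assumptions. Overall rate: p = f·c + (1 − f)·0.10.

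| f | c | p | P(success) |
|---|---|---|---|
| 0 | – | 0.100 | 0.047 |
| 0.10 | 0.50 | 0.140 | 0.185 |
| 0.10 | 0.70 | 0.160 | 0.287 |
| 0.10 | 0.95 | 0.185 | 0.430 |
| 0.20 | 0.50 | 0.180 | 0.401 |
| 0.20 | 0.70 | 0.220 | 0.624 |
| 0.20 | 0.95 | 0.270 | 0.828 |

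**4. If the untreated rate is well above 10%.** Every man enters with undetectable PSA, so many could stay below 0.20 without metformin. With an inert drug and no contamination, the current rule gives P(success) = 0.999 at an untreated rate of 50% and essentially 1 at 75%. Contamination then hardly changes the decision, but it still moves the estimate. With an illustrative untreated rate of 75% and c = 0.95, p = f·0.95 + (1 − f)·0.75:
- f = 0.10: 0.095 + 0.675 = 0.77
- f = 0.20: 0.190 + 0.600 = 0.79
- f = 0.30: 0.285 + 0.525 = 0.81

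These are response rates, not probabilities of false success. To see the effect on a reset decision, take a single-stage test of 75% with 35 men and success at 31 or more (an illustration, not the plan's design). Its type I error is 0.041 at 75%, and 0.070, 0.114 and 0.179 at true inert-drug rates of 77%, 79% and 81%.

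**The case against.** **The documents place radiotherapy after metformin.** The endpoint refers to PSA after surgery, the secondary endpoints concern therapy upon recurrence and salvage outcomes after metformin, and removed patients are referred to salvage treatment. This is good evidence of intent, and it suggests a drafting gap. But it screens no one out and changes no man's response status.

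**A reader might infer that contamination biases the result under any null.** The documents do not support that. Prior treatment is a feature of the enrolled population, and a reference rate from men with the same treatment mix would absorb it. The bias arises when the reference comes from a differently treated population, such as men treated by surgery alone. The plan gives no source for its 10%.

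**A reader might take 0.43 or 0.83 as the size of the harm.** Those figures combine an assumed 95% control rate with a 10% rate for all other men, which is hard to credit when everyone starts undetectable. They partly reflect that null, which is a separate problem. Likewise, three irradiated men would not be certain to meet the stage-1 bound by themselves: at 95% each, all three respond with probability 0.95³ = 0.86.

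**A reader might give prior GnRH treatment equal weight.** The washout and normal-testosterone conditions make it the weaker route, and testosterone is measured at entry and at about month 9. The documents do not show that these men's PSA is still suppressed. What stands is that the opening words of Exclusion Criterion 3 and its exception pull in opposite directions and must be reconciled.

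**Conclusion.** The point holds for radiotherapy. Followed as written, the plan counts PSA control by another treatment as a metformin response in this cohort, and the response rate is biased upward unless the reference rate comes from men with the same treatment mix.

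The direction is clear, but the size is not, because it depends on a co-treatment share and a control rate that the documents do not give. At a 10% share and the plan's own null, the false-success probability is 0.185 to 0.43 for control rates of 50% to 95%, against 0.047 without contamination. If the untreated rate is much higher than 10%, the go/no-go decision is already uninformative, and the remaining harm is to the estimate and any reset null: 2 to 6 percentage points in the 75% illustration. Resetting the null does not settle this by itself, because a reference rate cannot be chosen until the treatment mix of the counted men is defined.

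**What to change.** 1. Reconcile Criterion 4 with the endpoint wording, so that the 18 and 35 in the decision count are men whose undetectable PSA follows prostatectomy alone. Item 5 of the Pre-Enrollment Evaluation already supplies the history needed.
2. If previously irradiated or GnRH-treated men are enrolled, report them separately, outside the decision count. Reconcile the opening words of Exclusion Criterion 3 with its GnRH exception.
3. In the analysis, count a man who starts any other prostate cancer treatment before month 9 as a non-responder, including one removed at the PSA exit trigger and then treated. Record the start date of such treatment. This is a counting rule only and does not restrict the care he receives. Other handling is defensible, but it must be stated in advance.
4. Draw any revised null from men with the same treatment history as the counted men.

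**Cost.** One amendment. The sample size and bounds stay as they are. The pool for the decision count is somewhat smaller, so accrual may be slower. The non-responder rule gives a slightly lower, conservative response rate, because it also counts men who start other treatment while still undetectable.

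### Weight loss is a listed expected harm, but weight is scheduled only before enrolment, so change from baseline cannot be computed from the data the plan requires

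*Combined protocol and SAP*

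**What the plan says.** The Combined protocol and SAP mentions body weight in two places. Pre-Enrollment Evaluation, item 2, is a "Physical Examination including ECOG status, blood pressure, pulse, height, weight and BMI". The Expected AEs list, in the Risk section, has the entry "Weight loss (14% of metastatic prostate cancer patients", where the bracket closes.

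Study Evaluations brings men back "every three months for evaluation of study compliance, completion of study questionnaires, and blood draw". The items beneath it are a bottle check with a signed attestation, a "blood sample for evaluation of hematology and serum chemistry, insulin levels, total and free PSA, and Hemoglobin A1C", and the EPIC and MAX-PC questionnaires. The last item reads: "At the end of the study, at approximately 9 months, subjects will also be tested for insulin and testosterone levels".

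On reporting, AE Management says: "Adverse events will be recorded and monitored throughout the study, and the rates will be reported as part of the study end points". Analysis of Adverse Events describes monthly monitoring and adds that "the rates will be formally analyzed at the end of the first stage of the study". Protection against Risks provides for an adverse-event assessment at each three-monthly visit, without a method, grading scale or definition of weight loss.

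**The concern.** The plan records a starting weight, lists weight loss as something metformin may cause, and commits to reporting adverse-event rates. It then schedules no second weight. A harm that a scale would measure directly is left to whatever a man reports or to a weight that staff happen to take.

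At stake is the quality of one descriptive safety result. The cohorts are single-arm, so no control group would show whether weight loss had been under-recorded. AE Management itself says that adverse-event rates cannot be firmly predicted for these men, so the trial's own data are the main source for this population.

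**Working it through.** **1. The plan's own figure.** The plan calculates nothing for weight loss. The 14% is an outside rate with no derivation, so there is nothing to reproduce. The one design probability stated, 0.73 for early stopping, is the chance of 2 or fewer responders among 18 at a 10% response rate. The exact binomial value is 0.734, and weight does not enter it.

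**2. What each visit requires** (from Pre-Enrollment Evaluation, Study Evaluations and Protection against Risks):

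| Item | Before enrolment | Months 3, 6, 9 | Added at about month 9 |
|---|---|---|---|
| Weight, BMI | Yes | Not listed | Not listed |
| Physical examination | Yes | Not listed | Not listed |
| Blood tests | Yes | Yes | Insulin, testosterone |
| EPIC and MAX-PC | Yes | Yes | – |
| Adverse-event assessment | – | Yes, method not stated | – |

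**3. Change from baseline.** Let W0 be the weight before enrolment and Wt the weight at month t, with t = 3, 6, 9. Percent change is 100 × (Wt − W0) / W0, which needs both weights. The plan requires W0 once per man and none of the three values of Wt. So 0 of 3 changes per man can be computed from required data. Across Stage 1 (3 cohorts × 18 = 54 men) that is 0 of 3 × 54 = 162.

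**4. The adverse-event route.** A rate needs a case definition and a way of finding cases. Protection against Risks supplies neither for weight loss. Subject Capacity mentions self-reporting of symptoms, but only in explaining why full mental capacity is required. What remains is self-report or weights taken outside the schedule.

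**5. Size.** If nobody is wrongly counted, the reported rate is p × c, where p is the true rate and c the fraction of cases found. The only candidate for p is 14%, from metastatic patients, and Exclusion Criterion 1 removes metastatic disease. The documents give no value for c. The product cannot be derived.

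**The case against.** The strongest reply is that the visit list is not exhaustive. The adverse-event assessment is itself absent from Study Evaluations and appears only under Protection against Risks, so the absence of weight from the list does not prove that men will not be weighed. This stands as a limit on wording: weights may be taken. It does not close the gap, because nothing requires them, and optional weights may be incomplete or taken selectively.

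A second reply is that no decision uses weight. No response definition, stage rule, sample size or removal criterion refers to it. That is correct and keeps the point minor.

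A third is that, with no control arm, measured loss could not be separated from diet, ageing or disease. That is also true, but it concerns attribution to metformin. What the plan promises is a rate, and that rate can be better or worse measured.

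A fourth is that ECOG status, blood pressure and pulse are also not listed again after baseline, and that the plan never says baseline weight was taken for later comparison. Both are so. Weight differs in that its loss is on the plan's own list of expected harms.

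**Conclusion.** The point holds as a minor improvement to safety measurement. A listed expected harm has a required baseline and no required follow-up value, so its rate would depend on self-report or unscheduled weights. This assumes only that required data are those the plan writes down. The primary endpoints, sample size and decision rules are untouched.

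Four stronger readings are tempting but unsupported:

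- A reader might infer that weight loss is a named safety endpoint. Secondary Endpoints names safety and the incidence of serious adverse events. The commitment in AE Management covers adverse-event rates in general.
- A reader might infer that capture rests on unprompted recall. An assessment is scheduled at every visit; its method is simply not stated.
- A reader might infer that weight loss is the only listed harm open to objective measurement. Hypoglycemia and lactic acidosis can be assessed by laboratory test.
- A reader might put a number on the distortion. Assuming that 50% to 75% of cases are found, 14% × 0.50 = 7.0% and 14% × 0.75 = 10.5%. The capture range has no source in the documents and the 14% belongs to an excluded population. Even on those assumptions, 14% of 54 is 7.6 men, and the exact 95% interval for 8 of 54 is 6.6% to 27.1%, which contains both figures.

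**What to change.** In Study Evaluations, add body weight to the existing month 3, 6 and 9 visits. In the safety analysis, report for each cohort and visit the percent change from the pre-enrolment weight, the number of men weighed, and the proportion beyond a weight-loss threshold that the sponsor fixes in advance, alongside the reported adverse events. The threshold is for reporting only and implies no change to treatment or to the removal criteria.

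The cost is three extra data fields per man and about a minute per visit, with no additional visit, staff or test. At full enrolment in all three cohorts (3 × 35 = 105 men) that is at most 3 × 105 = 315 values.
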